2.1.1.10 Windows for multiple assessments

In order to summarize ECOG and other data collected over time (including unscheduled visits), the assessments will be time slotted. The following general rule will be applied in creating the assessment windows (except for ECOG, see [Section 2.6.1](#) for ECOG-specific rules): If more than one assessment is done within the same time window, the assessment performed closest to the target date will be used. If 2 assessments within a time window are equidistant from the target date, then the earlier of the 2 assessments will be used. If multiple assessments on the same date then the worst case will be used. Data from all assessments (scheduled and unscheduled), including multiple assessments, will be listed.

Time windows for ECOG assessments is listed in [Table 2-4](#).

2.2 Analysis sets

The Full Analysis Set (FAS) is comprised of all participants to whom study treatment has been assigned by randomization. According to the intent to treat principle, participants will be analyzed according to the treatment and strata they have been assigned to during the randomization procedure. The FAS will be the population for all efficacy analyses.

The Safety Set includes all participants who received at least one dose of study treatment (i.e. at least one dose of any component of alpelisib, fulvestrant, dapagliflozin + metformin XR, metformin XR). Participants will be analyzed according to the study treatment received, where treatment received is defined as the randomized treatment if the participant took at least one dose of that treatment or the first treatment received if the randomized treatment was never received. The safety set will be the analysis set for all safety analyses.

2.2.1 Patient classification

Participants may be excluded from the analysis sets defined above based on the protocol deviations entered in the database and/or on specific participant classification rules defined in [Table 2-1](#).

Table 2-1 Participant classification based on protocol deviations and non-PD criteria

Analysis set	Protocol deviation criteria leading to exclusion	Non-protocol deviation criteria leading to exclusion
FAS	No written informed consent	Not applicable
Safety set	No written informed consent	No dose of study treatment

2.2.2 Withdrawal of informed consent/opposition to use data/biological samples

Any data collected in the clinical database after a participant withdraws informed consent/opposition to use data/biological samples from all further participation in the trial, will not be included in any analysis. The date on which a participant withdraws full consent is recorded in the eCRF. When an end of treatment visit occurs after withdrawal of informed consent/opposition to use data/biological samples, the end of treatment disposition status and reasons are retained.

Additional data for which there is a separate informed consent (such as pregnancy outcomes reporting consent, if applicable), collected in the clinical database without having obtained that consent will not be included in the analysis.

Any data that will be excluded will be identified by the presence of the appropriate protocol deviation criterion.

2.2.3 Subgroups of interest

No subgroup analysis will be performed.

2.3 Participant disposition, demographics and other baseline characteristics

Demographic data will be summarized descriptively by treatment group for the FAS.

Categorical data will be presented as frequencies and percentages. For continuous data, mean, standard deviation, median, minimum, and maximum will be presented. For selected parameters, 25th and 75th percentiles will also be presented.

2.3.1 Participant disposition

Enrollment by country and center will be summarized for all screened participants and also by treatment group using the FAS. The number (%) of randomized and treated participants included in the FAS will be presented overall and by treatment group. The number (%) of screened but not-randomized participants and the reasons for screening failure will also be displayed. The number (%) of participants in the FAS who are still on treatment, who discontinued the study phases and the reason for discontinuation will be presented overall and by treatment group.

The following summaries will be provided (with % based on the total number of FAS participants):

- Number (%) of participants who were randomized (based on data from IRT system)
- Number (%) of participants who were randomized but not treated (based on ‘Study Treatment’ and “Study Treatment Summary” eCRF not completed for any study treatment component)
 - Primary reason for not being treated (based on ‘Treatment disposition’ eCRF)
 - Number (%) of participants who were treated (based on ‘Study Treatment’ or “Study Treatment Summary” eCRF of each study treatment component completed with non-zero dose administered)
 - Number (%) of participants who are still on-treatment (based on the ‘Treatment disposition’ eCRF not completed);
 - Number (%) of participants who discontinued the study treatment phase (based on the ‘Treatment disposition’ eCRF)
- Primary reason for study treatment phase discontinuation (based on the ‘Treatment disposition’ and ‘Subject status’ eCRFs)
- Number (%) of participants who have entered the post-treatment follow-up (based on the ‘Treatment disposition’ and ‘Subject status’ eCRFs);
 - Number (%) of participants who have discontinued from the post-treatment follow-up (based on the ‘Post-treatment follow-up disposition’ eCRF);
 - Reasons for discontinuation from the post-treatment follow-up (based on Post-treatment follow-up disposition’ eCRF);

Protocol deviations

All protocol deviations will be listed.

2.3.2 Basic demographic and background data

All demographic data will be summarized and listed for the FAS by treatment group. Categorical data (e.g. race) will be summarized by frequency counts and percentages; the number and percentage of participants with missing data will be provided. Continuous data (e.g. age, weight, etc.) will be summarized by descriptive statistics (N, mean, standard deviation, median, minimum and maximum). BMI (kg/m^2) will be calculated as $\text{weight}[\text{kg}] / (\text{height}[\text{m}]^2)$ using weight at baseline.

2.3.3 Other

All data collected at baseline will be listed as appropriate.

2.4 Treatments (study treatment, rescue medication, concomitant therapies, compliance)

2.4.1 Study treatment / compliance

Listings of each component of study treatment with dose reductions, interruptions or permanent discontinuations, and the reasons will be provided by treatment group based on the safety set. Details of the derivations and summaries are provided in the following sections.

2.4.2 Dose reductions, interruptions or permanent discontinuations

Dose administered (mg) and dosing frequency from the “Study Treatment” or “Study Treatment Summary” eCRF of each component of study treatment will be used to determine the dose reductions, titrations and interruptions.

‘Dose permanently discontinued’ box ticked from the “Study Treatment” or “Study Treatment Summary” eCRF of each component of study treatment will be used to determine permanent discontinuation.

Dose reductions

For alpelisib, a dose reduction is defined as a decrease in dose from the previous non-zero dose to another non-zero dose less than the protocol planned starting dose, even if this decrease has been directly preceded by an interruption. For example, in the sequence 300 mg daily to 0 mg to 250 mg daily, the 250 mg dose will be counted as a reduction. On the other hand, if the dose decrease is followed by an interruption, with the dose resuming at the same level prior to the interruption (e.g. in the sequence 250 mg daily to 0 mg to 250 mg daily), the second dose decrease will not be counted as dose reduction.

If, due to a dosing error, a participant receives a higher than planned starting dose and moves down to the planned starting dose then this is not considered a dose reduction. However if the dose change is from a higher than planned starting dose down to a lower than protocol planned starting dose, then this is considered a dose reduction (e.g. in the sequence: 350 mg daily to 300 mg daily to 250 mg daily; 250 mg is considered a dose reduction).

If, due to a dosing error, a participant receives a lower than previous non-zero dose and resumes later at the protocol specified dose reduction, then the lower dose received due to dosing error

and protocol specified dose reduction are dose reductions (e.g. in the sequence 300 mg daily to 200 mg daily to 250 mg daily, then 200 mg and 250 mg are considered dose reductions).

If, due to a dosing error, a participant receives a lower than previous non-zero dose and resumes later at a lower than previous non-zero dose, then 2 dose reductions will be counted (e.g. in the sequence 300 mg daily to 250 mg daily to 200 mg daily, 250 mg and 200 mg are dose reductions).

For fulvestrant, dapagliflozin and metformin XR, the reduction counting rules from above apply.

Table 2-2 Examples of Dose Reduction for alpelisib

Sequence	Reduction
With dose change	
300 mg daily to 250 mg daily to 0 mg to 250 mg daily	1 reduction (the 1 st 250 mg)
300 mg daily to 300 mg daily to 0 mg to 250 mg daily	1 reduction (250 mg)
300 mg daily to 0 mg to 250 mg daily	1 reduction (250 mg)
With interruption	
300 mg daily to 0 mg to 300 mg daily	0 reductions
With dosing error	
300 mg daily to 250 mg daily to 200 mg daily*	2 reductions (250 mg, 200 mg)
300 mg daily to 200 mg daily* to 300 mg daily	1 reduction (200 mg)
300 mg daily to 200 mg daily* to 250 mg daily	2 reductions (200 mg, 250 mg)
300 mg daily to 400 mg daily* to 350 mg daily*	0 reductions since 400 mg and 350 mg are dose escalations not reduction
300 mg daily to 150 mg daily* to 300 mg daily	1 reduction (150 mg)
With dosing error at the 1st administration	
150 mg daily* to 300 mg daily	1 reduction (150 mg)
150 mg daily* to 0 mg to 150 mg daily* to 300 mg daily	1 reduction (150 mg)
150 mg daily* to 300 mg daily to 0 mg to 250 mg daily	2 reductions (150 mg and 250 mg)

*dosing error

Dose interruptions

An interruption is defined as a 0 mg dose on one or more days between two non-zero dosing records. Any two or more consecutive zero doses of alpelisib (e.g. in the sequence 300 mg daily to 0 mg to 0 mg to 300 mg daily) or other study treatment component (fulvestrant, dapagliflozin or metformin XR) will be counted as 1 interruption if the reasons for these two consecutive dose interruption are the same. It will be counted as two different interruptions only if the reasons are different. For participants who have dose interruption checked in the eCRF but

never resume with a non-zero dose, the dose interruption will not be counted. For example, in the sequence of 300 mg daily to 0 mg (dose interruption) to 0 mg (dose permanently discontinued), the 0 mg (dose interruption) will not be counted as a dose interruption.

Note: The last zero dose of any study treatment component at permanent discontinuation is not considered as a dose interruption.

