### 6.6.2.2 Dose titration guideline for dapagliflozin + metformin XR

The starting dose of dapagliflozin + metformin XR is 5 mg dapagliflozin + 500 mg metformin XR orally once daily. If tolerated after several days, increase to dapagliflozin 5 mg +1000 mg metformin XR once daily in the morning with food. If tolerated, increase to dapagliflozin 10 mg +1000 mg metformin XR once daily in the morning with food. If tolerated, increase to the maximum daily dose of dapagliflozin 10 mg + 2000 mg metformin XR once daily in the morning with food. If not tolerated, reduce to prior tolerated dose. Titrate to the MTD over a period of 3 weeks as described in [Table 6-5](#).

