NCI	National Cancer Institute
NE	Not evaluable
OL	Open-label
ORR	Overall response rate
PD	Progressive disease
PDI	Planned dose intensity
PFS	Progression-free survival
PIK3CA	Phosphoinositide-3-kinase catalytic subunit alpha

PR	Partial response
PT	Preferred term
QTcF	Corrected QT interval (corrected by Fridericia's formula)
RDI	Relative dose intensity
RECIST	Response Evaluation Criteria In Solid Tumors
SAE	Serious adverse event
SAP	Statistical Analysis Plan
SD	Stable disease
SMQ	Standardized MedDRA queries
SOC	System organ class
TA	Tumor assessment
TBIL	Total bilirubin
UNK	Unknown
WHO	World Health Organization
XR	Extended Release

1 Introduction

This document describes the detailed statistical methodology to be used for the clinical study report (CSR) for the analysis of study CBYL719C2202, a Phase II, multicenter, randomized, open-label, active-controlled trial designed to assess the safety and efficacy of the combination of dapagliflozin plus metformin XR compared to metformin XR alone during treatment with alpelisib plus fulvestrant in participants with HR-positive, HER2-negative advanced breast cancer with a PIK3CA mutation following progression on or after endocrine-based therapy.

The content of this SAP is based on the CBYL719C2202 protocol amendment 1 released on 06-Aug-2021. All decisions regarding analyses, as defined in this document, have been made prior to the database lock. Due to the permanent halt of recruitment and early termination of study, the primary analysis will not be conducted. Further changes to the protocol specified analyses are listed in [Section 4](#).

CSR deliverables (shells for tables, figures, listings) and further programming specifications are described in the Tables, Figures & Listings (TFL) shells and Programming Datasets Specification (PDS), respectively.

Statistical Outputs and corresponding data structures required for Clinical Disclosure of Trial Results will also be described in the Tables, Figures & Listings (TFL) shells and Programming Datasets Specification (PDS), respectively.

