3.1 Primary endpoint(s)

The sample size calculation is based on the primary endpoint occurrence of severe hyperglycemia. The hypotheses to be tested and details of the testing strategy are described in [Section 2.5.2](#).

The incidence of severe hyperglycemia adverse events over the first eight weeks of alpelisib plus fulvestrant treatment in the study treatment arm B (i.e. prophylactic metformin XR alone) is assumed to be 40% based on data from the SOLAR-1 study in HR-positive, HER2-negative, advanced breast cancer participants with a PIK3CA mutation treated with alpelisib plus fulvestrant.

It is expected that treatment with prophylactic dapagliflozin plus metformin XR will result in a 20% reduction in the incidence rate. Approximately 124 participants (62 in each arm) will be required to detect a 20% difference in incidence rate with 80% power using the difference of proportion test at a one-sided 5% level of significance ([Table 3-1](#)). Assuming a 5% dropout rate (participants without adequate assessment of glucose laboratory values per protocol from Cycle 1 Day 8 to Cycle 3 Day 8) at the time of primary analysis, approximately 132 participants will need to be randomized to the two treatment arms in a 1:1 fashion.

Table 3-1 Sensitivity of power to changes in assumptions for N=124

Expected reduction in incidence rate	Observed reduction in incidence rate	Power
20%	30%	99.2%
	25%	93.8%
	20%	79.1%
	15%	56.1%
	10%	32.0%
	5%	14.2%

Note: Simulations are performed in East 6.4 with number of simulations = 100,000 and randomization seed = 2020.

4 Change to protocol specified analyses

Due to the permanent halt of recruitment and early termination of study, the primary analysis will not be conducted. Instead,

- the primary endpoint will only be summarized descriptively without any supplementary analysis.
- the secondary efficacy endpoint, PFS will only be listed without summaries.
- the secondary efficacy endpoints ORR and CBR will only be listed without summaries.
- there will be no subgroup analyses for efficacy and safety endpoints
- the study treatment such as exposure and dose intensity will only be listed without summaries.
- for safety endpoints, only adverse events, deaths and serious adverse events will be summarized. Other safety endpoints will only be listed for participants with notable values.

5 Appendix

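### The dose-reduction rule in SAP 2.4.2 cannot register an error-free step down between protocol dose levels for dapagliflozin or metformin XR

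*SAP*

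**What the plan says.** SAP 2.4.2 gives its definition for alpelisib: "a decrease in dose from the previous non-zero dose to another non-zero dose less than the protocol planned starting dose". It then closes the prose rules with one sentence for the other components: "For fulvestrant, dapagliflozin and metformin XR, the reduction counting rules from above apply". No other reference dose is given for those drugs. The opening of SAP 2.4.2 mentions titrations alongside reductions and interruptions, and Protocol 12.3 does the same, but the SAP contains no rule for counting a titration.

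The resulting output is set in SAP 2.4.1: "Listings of each component of study treatment with dose reductions, interruptions or permanent discontinuations, and the reasons will be provided by treatment group". SAP Section 4 limits the rest: "the study treatment such as exposure and dose intensity will only be listed without summaries".

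The starting doses are in Protocol 6.1.1, 6.3.2.3 and 6.3.2.4: 500 mg metformin XR in Arm B, and 5 mg dapagliflozin with 500 mg metformin XR in Arm A. Both regimens are then titrated up. Protocol 6.6.2.2 foresees a downward step for intolerance: "If not tolerated, reduce to prior tolerated dose. Titrate to the MTD over a period of 3 weeks". Tables 6-4 and 6-5 print the same instruction beside the top level. Protocol Table 2-1 and SAP Table 1-1 make dose reductions of every drug component part of the tolerability endpoint.

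**The concern.** The definition has two conditions: the dose must fall, and the new dose must lie below the starting dose. The second condition does no harm for a drug that starts at its top level. For a drug that starts at its bottom level, no protocol dose can meet it. The rule was evidently built for alpelisib and carried to two drugs with the opposite dosing pattern.

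At stake is the derived record of reductions, with reasons, for the two drugs that the randomized comparison is about. A reader of the study report who sees no reductions for dapagliflozin or metformin XR could conclude that nobody had to step down, when the derivation could not have shown it.

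**Working it through.** **Rule.** Let d be the new non-zero dose, p the previous non-zero dose and S the protocol starting dose. The main definition counts a reduction when d < p and d < S. Zero doses in between are skipped.

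**Reproducing SAP Table 2-2 (S = 300 mg).** The stated counts for the 12 sequences are 1, 1, 1, 0, 2, 1, 2, 0, 1, 1, 1, 2. The main definition alone gives 1, 1, 1, 0, 2, 1, 1, 0, 1, 0, 0, 1. It matches all four rows without a dosing error and four of the eight error rows. The other four rows (300 to 200* to 250, and the three with an error at first administration, such as "150 mg daily* to 300 mg daily") need the dosing-error rules. With these added, all 12 rows agree. The row 300 to 400* to 350* shows that the starting-dose condition is active: 350 < 400, but 350 is not < 300, so the SAP counts 0.

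**Applying the rule to each ladder.** With k distinct levels there are k(k−1)/2 downward moves. Levels come from Protocol Tables 6-2, 6-4 and 6-5.

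| Drug | Levels (mg) | S | Downward moves | Counted |
|---|---|---|---|---|
| Alpelisib | 200, 250, 300 | 300 | 3 | 3 |
| Metformin XR, Arm B | 500, 1000, 1500, 2000 | 500 | 6 | 0 |
| Metformin XR, Arm A | 500, 1000, 2000 | 500 | 3 | 0 |
| Dapagliflozin, Arm A | 5, 10 | 5 | 1 | 0 |

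When S is the highest level, every decrease gives d < S. When S is the lowest, d < S is never true. An interruption between the two doses changes nothing.

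**Steps the titration tables spell out.**
- Table 6-4, metformin XR 500–1000–1500–2000–1500: 1500 < 2000 holds, 1500 < 500 does not. Count 0.
- Table 6-5, metformin XR 500–1000–1000–2000–1000: 1000 < 2000 holds, 1000 < 500 does not. Count 0.
- Table 6-5, dapagliflozin 5–5–10–10–10: no decrease, so 0 under any rule.

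So 0 of the 2 explicit steps are counted.

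**Dosing errors (marked \*).** Two clauses, including the one that begins where "a participant receives a lower than previous non-zero dose and resumes later at a lower than previous non-zero dose", do not repeat the starting-dose condition. Metformin XR 2000–1000\*–2000 therefore gives 0 under the main definition but 1 if the clause is read literally; 2000–1000\*–1500 gives 0 or 2. An erroneous step can be counted on one reading while a genuine tolerability step cannot.

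**Checking the replacement rule given under the fix.** It counts 6 of 6, 3 of 3 and 1 of 1 for the titrated ladders, and 1 for each explicit metformin XR step. Alpelisib keeps its current rule and stays at 3 of 3. Run on Table 2-2, the replacement also reproduces 12 of 12 rows. For errors it gives: 2000–1000\*–2000, 1; 2000–1000\*–1500, 2; 1000–2000\*–1000, 0; 500–1500\*–1000, 0; 1000–2000\*–500, 1; first dose 250\*–500, 1. Uninterrupted up-titration gives 0.

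**The case against.** The strongest reply is that these steps are titration, not reduction. The protocol puts dose modifications in 6.6.1 and antihyperglycemic titration in 6.6.2, and both documents name titrations separately. On that view, leaving a down-titration out of the reductions is a design choice. But the protocol's own instruction is to reduce the dose, the SAP has no titration rule, and SAP 2.4.1 lists no titrations. The step would be missed under either label. What stands is that the SAP must choose a label, and the fix does so.

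One could also argue that the starting-dose condition belongs to alpelisib only, because the definition opens with that drug. If the carry-over sentence leaves out the definition, however, dapagliflozin and metformin XR have no definition of a reduction at all.

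Three points on consequence stand. Raw dose records may still show the sequence, and the layouts and further specifications sit outside these documents ("CSR deliverables (shells for tables, figures, listings) and further programming specifications are described in the Tables, Figures & Listings (TFL) shells", and a programming datasets specification). Protocol 10.1.1 records the action taken with study treatment for each adverse event, including a dose change, so some steps may surface in the adverse event listings. And the one downward step printed for Arm A leaves dapagliflozin unchanged, so the practical weight falls mainly on metformin XR.

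**Conclusion.** The rule is wrong as written for dapagliflozin and metformin XR. For dosing on the protocol ladder without dosing errors, it yields no reductions for either drug, whatever participants actually did. This rests on reading the carry-over sentence as including the definition, which is the only reading that gives these drugs one. The 0-of-6, 0-of-3 and 0-of-1 figures describe the reach of the rule over all possible moves, most of which the protocol does not describe; they do not predict how many participants would be affected.

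Severity is minor. The damage is confined to a derived listing for one part of a secondary tolerability endpoint. The primary endpoint is untouched, and no summary or test depends on this rule after early termination. Fulvestrant is not a problem, because the protocol allows only one dose of it.

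**What to change.** In SAP 2.4.2, replace the carry-over sentence with:

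> For fulvestrant, the rules above apply. For dapagliflozin and metformin XR, each counted separately, a dose reduction is any decrease from the previous non-zero dose to a lower non-zero dose, including during titration or directly after an interruption. After a dose given in error above the last prescribed dose, a decrease counts only if the new dose is below that last prescribed dose. The rules above for a dose given in error below the previous non-zero dose, and Table 2-2 for a first dose given in error below the starting dose, also apply.

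Keep the alpelisib rules as they are. This settles that a down-titration is listed as a reduction. It changes a derivation only and says nothing about which dose is right.

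The cost is one SAP passage and one derivation condition for two drugs. Protocol 6.1 already requires prescribed dosages and all dose changes to be recorded on the eCRF, so no new data collection is needed. SAP 2.4.2 names different eCRF pages from Protocol 6.1, so the programmer should confirm which page holds the prescribed dose needed for the error clause.
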